5.4 Efficacy variables

5.4.1 Primary efficacy variable(s): ARR up to EOS

The primary endpoint is the Annualized Relapse Rate (ARR) up to EOS, based on confirmed relapses according to the treating neurologist / principal investigator. ARR is defined as the number of confirmed relapses per subject-year.

A confirmed relapse is defined as a record with 'Relapse meeting the criteria for a confirmed relapse?' answered 'Yes' on the 'Relapse Summary' eCRF. All confirmed relapses from randomization up to EOS will be included in the analysis.

For the statistical analysis of ARR, the following data will be used:

- Number of confirmed relapses from date of randomization up to EOS date;
- Length of observation expressed in years, defined as: [EOS date – date of randomization + 1] in days, divided by 365.25.

The logarithm of the length of observation up to EOS will be used as an offset variable in the primary efficacy and sensitivity analyses.

Confirmed relapses 'from date of randomization up to EOS date' includes all confirmed relapses unless starting prior to randomization.

5.4.1.1 General derivation details for relapses

A relapse (confirmed or unconfirmed) is identified from the ‘Relapse Summary’ eCRF with ‘Did the subject experience a relapse’ ticked as ‘Yes’. For each relapse the corresponding start and end date/time, as well as outcome, treatment with corticosteroids, action taken with study drug and need for hospitalization, and whether an EDSS was completed are recorded. For relapses with completed EDSS it is collected whether it qualifies as a confirmed relapse (see definition details for primary efficacy variable above). A relapse which is not a confirmed relapse is considered an ‘unconfirmed relapse’.

Relapses ‘from date of randomization up to EOS date’ include all relapses unless starting prior to randomization.

Note: Relapses with missing start date are considered to have started on randomization date for analysis. Relapses with partial start date are considered to have started at the lower limit (but earliest on randomization date).

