5.4.2.2 Time to first confirmed relapse

The time to first confirmed relapse (in days) is defined as [Date of first confirmed relapse – Date of randomization + 1] in days.

Subjects without any confirmed relapses will be censored at the EOS date, and the time is defined as [Date of EOS – Date of randomization + 1] in days.

Derivation of confirmed relapses from randomization up to EOS is detailed in Section 5.4.1. Among these confirmed relapses, the earliest relapse start date is the ‘Date of first confirmed relapse’. For analysis the variable is displayed in weeks: variables in days divided by 7.

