9.6 Analysis of the primary efficacy variable

9.6.1 Hypothesis and statistical model

A generalized linear model with negative binomial distribution for the number of confirmed relapses will be assumed as described in Section 10.1.

Two-sided hypotheses are expressed in terms of the model parameters $\mu_{\text{Ponesimod}}$ and μ_{Placebo} . The primary null hypothesis is that the ARR (μ) does not differ between ponesimod and placebo. The alternative hypothesis is that the ARR differs between ponesimod and placebo.

$$\begin{aligned} H_{0, \text{ARR}}: \mu_{\text{Ponesimod}} - \mu_{\text{Placebo}} &= 0 \\ &\text{vs} \\ H_{1, \text{ARR}}: \mu_{\text{Ponesimod}} - \mu_{\text{Placebo}} &\neq 0 \end{aligned}$$

The null hypothesis will be tested by a two-sided Wald test within the negative binomial regression model [see Section 9.6.2], with a two-sided significance level of 0.05.

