12 HANDLING OF MISSING/INCOMPLETE DATE AND TIME FIELDS

In the following, ‘lower limit’ and ‘upper limit’ refer to the minimum or maximum, respectively, of a possible date. For example, if the day is missing, the lowest limit is the first day of the given month and the upper limit is the last day of the given month. If the day and month are missing, the lower limit refers to the first day of the given year and the upper limit to the last day of the given year. *The earliest and the latest dates refer to the first or last date, respectively, when ordered in sequence.*

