12.2 Relapse

Type of date/time	Date/time is incomplete	Date/time is missing
Relapse start date (collected on 'Relapse Summary' eCRF)	Maximum of lower limit and randomization date Unless upper limit is prior to randomization date, then upper limit	Randomization date

eCRF = electronic case report form.

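### SAP 5.4.1.1 and 12.2 disagree on a relapse whose partial start date lies wholly before randomization: one counts it on Day 1 in the primary ARR, the other excludes it

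*SAP*

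**What the plan says.** Section 5.4.1.1 takes relapses from the Relapse Summary eCRF and gives two imputation rules for the start date. For a completely missing date: "Relapses with missing start date are considered to have started on randomization date for analysis". For a partial date: "Relapses with partial start date are considered to have started at the lower limit (but earliest on randomization date". The second rule carries no exception.

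Section 12.2 names the same eCRF and the same field. Its rule for an incomplete date is "Maximum of lower limit and randomization date Unless upper limit is prior to randomization date, then upper limit". For a completely missing date it also uses the randomization date, so the two sections agree there. Section 12 defines the terms; when only the day is missing, "the upper limit is the last day of the given month".

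The imputed date decides inclusion. Under Section 5.4.1 the on-study count "includes all confirmed relapses unless starting prior to randomization", and Section 5.4.1.1 repeats this for relapses of any kind. Section 5.4.2.2 uses the same events for time to first confirmed relapse: "Among these confirmed relapses, the earliest relapse start date is the" date of the first event.

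**The concern.** When the whole of a partial date precedes randomization, the two sections give the same record opposite inclusion status. Under 5.4.1.1 the imputed start equals the randomization date, so the exclusion of relapses starting before randomization no longer applies. A relapse known to be pre-study then becomes an on-study event.

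Three analyses are affected: the primary ARR on confirmed relapses (9.6.2), the supplementary ARR on all relapses (9.6.4.1) and the Kaplan-Meier summary of time to first confirmed relapse (9.7.2). In the last of these the false event is a first relapse at 1 day. The primary comparison is still a formal test, "with a two-sided significance level of 0.05", and Section 9.6.3 plans no sensitivity analysis that would expose the difference.

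A programmer cannot tell which rule to follow. Section 5 says that it contains the derivation specifications. Other parts of it send the reader to Section 12 for dates (5.2.3 to 12.1 for therapies, 5.5.1 to 12.3 for adverse events), but 5.4.1.1 does not refer to 12.2.

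**Working it through.** The SAP gives no figure on this point to reproduce. The check has two parts: the rules on test dates, then the size of one misassigned event.

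**Rules.** Let L and U be the lower and upper limits of the partial date and R the randomization date.

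- 5.4.1.1: start = max(L, R).
- 12.2: start = U if U < R; otherwise max(L, R).
- Counted if start ≥ R (5.4.1).

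With R = 15 March 2018:

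| Recorded start | 5.4.1.1 | 12.2 |
|---|---|---|
| February 2018 | 15 Mar 2018, Day 1, counted | 28 Feb 2018, excluded |
| 2017 (year only) | 15 Mar 2018, Day 1, counted | 31 Dec 2017, excluded |
| March 2018 | 15 Mar 2018, counted | 15 Mar 2018, counted |
| May 2018 | 1 May 2018, counted | 1 May 2018, counted |
| 2018 (year only) | 15 Mar 2018, counted | 15 Mar 2018, counted |

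The rules differ only when U < R, and there they always give opposite inclusion results.

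**Size of one misassigned relapse.** From the SAP: 136 subjects randomized 1:1, enrolment from March 2017, termination decided on 26 November 2019, EOT visit within 8 weeks, follow-up visit about 30 days after the last dose. Assumed: uniform accrual from 15 March 2017 to 26 November 2019, last contact about 20 February 2020 (56 + 30 = 86 days after the decision), equal person-time per arm, ARR 0.15 to 0.30.

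- Mean follow-up = 986/2 + 86 = 579 days = 1.59 years.
- Total = 136 × 1.59 = about 216 subject-years. A lower value of 170 is assumed to allow for dropout.
- Relapses per arm = subject-years × ARR / 2. Low: 170 × 0.15 / 2 = 12.8. High: 216 × 0.30 / 2 = about 32.
- The person-time denominator does not change, so one extra event raises the arm's raw ARR by 1/events: 1/12.8 = 7.8% to 1/32 = 3.1%.

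A second set of assumptions (68 per arm, mean follow-up 1.0 to 1.5 years, ARR 0.15 to 0.35) gives 10.2 to 35.7 events per arm, so 9.8% to 2.8%.

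The raw rate ratio moves by the same factor: up if the extra event is in the ponesimod arm, down if in the placebo arm. For scale, with equal events in both arms and Poisson variation, the standard error of the log rate ratio is √(2/12.8) = 0.40 to √(2/32) = 0.25. The shift is ln(1.078) = 0.075 to ln(1.031) = 0.031, about 0.1 to 0.2 standard errors. Overdispersion would make that fraction smaller.

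**The case against.** The strongest reply is that the conflict is narrow and will hardly ever be triggered. The sections share a core rule, and 12.2 adds one exception. A relapse dated wholly before randomization is known to be pre-study without imputation. On that view the sentence in 5.4.1.1 excluding pre-randomization relapses removes it first, and the imputation note serves only relapses whose status is uncertain.

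The data flow also works against such a record. Prior relapses are collected on the separate MS History - Relapse form. Relapse visits run from Day 1 to EOS. A relapse within 30 days before the baseline EDSS, or between that assessment and randomization, is an exclusion criterion. Confirmation status is collected only when an EDSS was completed, and an EDSS more than 7 days after symptom onset is a listed deviation. Time to first confirmed relapse is exploratory and only summarized descriptively. Nothing suggests that such records would favour one arm.

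The points on rarity and on the absence of a directional bias stand. The reading that removes the conflict does not: 5.4.1.1 states no such order, and its note defines when a partially dated relapse is taken to have started, which is the input to the exclusion. Section 12.2 spells out this very case, so its authors did not treat the order as self-evident.

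**Conclusion.** The contradiction is real and concerns which events enter the primary endpoint. Read literally, 5.4.1.1 counts a relapse that its own recorded date places before randomization; 12.2 excludes it. The SAP does not rank the two rules.

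The practical effect is probably small. It needs a record on the on-study relapse form with a partial date wholly before randomization, and the SAP gives no count of these. Conditional on one such record, the arm's raw ARR and the raw rate ratio move by about 3% to 8% under the stated follow-up and ARR assumptions (2.8% to 9.8% under the second set), which is well inside sampling error. It should still be corrected, because the event rule for the primary endpoint should have only one reading.

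**What to change.** In 5.4.1.1, replace the sentence on partial start dates with the 12.2 rule: use the later of the lower limit and the randomization date, unless the upper limit falls before randomization, in which case use the upper limit and leave the relapse out of on-study counts. Have 5.4.1, 5.4.1.2.1 and 5.4.2.2 refer to 12.2 as the only rule for this field. Section 12.2 is the one to keep because it excludes only relapses whose latest possible date precedes randomization, which fits the count from randomization defined in 5.4.1. The separate partial-date rule in 5.4.2.1, used for disability confirmation, serves another purpose and can stay.

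The cost is one sentence plus cross-references, with no new data. If programs already exist, the relapse listing planned in 9.6.4.1 can be searched for partial start dates before randomization to see whether any record is affected.

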5.4.1.2 Variables for supplementary analyses of primary endpoint

5.4.1.2.1 ARR up to EOS for all relapses

The variable considers all relapses (confirmed and unconfirmed) up to EOS:

- The subject’s number of all relapses from date of randomization up to date of EOS;
- Length of observation expressed in years, defined as: $[\text{EOS date} - \text{date of randomization} + 1]$ in days, divided by 365.25.

5.4.2 Secondary efficacy variables

5.4.2.1 Time to 12-week confirmed disability accumulation (CDA) up to EOS

Time to first 12-week CDA is defined as the time from start date of the first onset of 12-week CDA minus date of randomization + 1 in days. Subjects without 12-week CDA are censored, following the rules below. It is assessed from baseline up to EOS.

Assessing disability by EDSS

Disability as measured by EDSS is assessed in all subjects at screening, baseline, and thereafter at scheduled visits every 12 weeks until the end of study. Additional EDSS assessments for individual patients may be conducted between scheduled visits (i.e., during an MS relapse). The EDSS is a disability scale that ranges from 0 (normal) to 10.0 (death) in 0.5-point steps (1-point step from 0 to 1). It is based on standard neurological examination in conjunction with observations concerning ambulation. For analysis the overall EDSS score as reported by the investigator from the eCRF is considered (Field: ‘Expanded disability status scale’).

EDSS increase criteria for disability accumulation

The following criteria for an increase in EDSS in derivation of disability accumulation apply:

- Increase of at least 1.5 in EDSS for subjects with a baseline EDSS score of 0;
- Increase of at least 1.0 in EDSS for subjects with a baseline EDSS score of 1.0 to 5.0;
- Increase of at least 0.5 in EDSS for subjects with a baseline EDSS score ≥ 5.5 ;

where baseline EDSS is defined as the last available EDSS score prior to or on the date of randomization.

12-week CDA

A 12-week CDA is an increase in EDSS as compared to baseline according to the criteria above which is confirmed at a scheduled visit after 12 weeks. The increase needs to be persistent at all EDSS assessments (scheduled or unscheduled) between onset (first EDSS increase in the considered period) and confirmation. 12-week CDA is assessed sequentially up to the last available EDSS assessment for a subject in the study following the algorithm detailed below.

Disability progression can only be confirmed at a scheduled visit, where the EOT (Up to Week 156 or earlier or premature EOT visit), and FU visits count as scheduled visits, outside of an ongoing relapse. In this context, relapse duration is defined as period between start date (inclusive) and end date (exclusive) if available and limited to 90 days from onset if end date is not available or duration is longer than 90 days.

Algorithm for deriving 12-week CDA

1. For all post-baseline EDSS assessments (scheduled or unscheduled) assess if the absolute change from baseline meets the EDSS increase criteria for disability accumulation, described above. Start with the first EDSS assessment that meets the criteria for EDSS increase. Onset date of the corresponding potential 12-week CDA is the EDSS assessment date.
2. Confirmation of EDSS increase:
 - a. An EDSS increase of a potential 12-week CDA has to be confirmed by an EDSS increase at a scheduled visit, at least 70 days*, from the onset date of the potential 12-week CDA.

* Note: As visits are scheduled every 12 weeks with a time window of ± 7 days for conducting the EDSS assessment, the minimum per-protocol allowed time difference between two EDSS assessments scheduled 12 weeks apart is 70 days (12 weeks = 84 days minus a 7-day visit time window for each of the 2 visits, i.e., 84 days – 14 days = 70 days).

EDSS assessments conducted during a relapse, i.e., from relapse start date (inclusive) to minimum of relapse end date and relapse start date + 90 days (exclusive) are not considered for confirmation.

If an EDSS increase cannot be confirmed due to no available EDSS assessment, but the subject dies due to MS (experiences a relapse with outcome death, or death with reason 'Multiple sclerosis') the CDA is also considered confirmed, with confirmation date being the death date and onset date the initial EDSS increase.

- b. A confirmed EDSS increase as per (a) is considered persistent if every EDSS score available (scheduled or unscheduled) between the onset and the confirmation date of a potential 12-week CDA meets the EDSS increase criteria. The initial EDSS increase is considered a 12-week CDA.

If any EDSS from onset to confirmation does not meet the EDSS increase criteria, the increase is not persistent and the initial EDSS increase is not considered a 12-week CDA.

3. Repeat step 2 for all EDSS assessments with an EDSS increase as per the criteria above for disability accumulation, starting with the first possible onset, by date, up to the last possible onset. Once a 12-week CDA is identified the algorithm can stop.
4. If at none of the assessments a 12-week CDA is identified, but the subject dies due to MS (experiences a relapse with outcome death) the subject is considered to have a 12-week CDA with onset date being the death date.
5. If no 12-week CDA is identified, the subject is considered censored with the censoring date derived according to the rules below.

Censoring

Censoring date is defined as: Date of last EDSS assessment without an EDSS increase. Time to censoring is defined as censoring date minus date of randomization + 1.

Subjects without post-baseline assessment are censored on randomization date. Similar, subjects without CDA who have only EDSS assessments with an EDSS increase that cannot be confirmed, are censored on randomization date. For subjects without baseline EDSS score, missing values are assigned.

Handling of missing dates

Missing dates for EDSS assessments will be imputed as follows:

- Partial date: Maximum of 'lower limit', 'previous scheduled EDSS assessment according to the visit label' + 1 day (if available), and 'randomization date'.
- Missing date: do not impute and exclude from analysis.

Missing dates for relapse start and end dates will be handled as follows:

- Partial or missing relapse end date with available relapse start date: use relapse start date + 90 days or upper limit of partial end date if earlier.
- Partial relapse start date: If only day is missing, consider the relapse to have started on the last day of the month (or on relapse end date – 1 day if earlier) and ended 60 days later or at (upper limit of a partial) relapse end date, if earlier. If the month or year are missing the relapse does not lead to non-consideration of an EDSS assessment.
- Missing relapse start date: Corresponding relapse does not lead to non-consideration of an EDSS assessment. Do not consider imputed relapse start dates.

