5.4.4 Other clinical efficacy variables

5.4.4.1 Time to 24-week CDA

The derivation of the variables for Time to 24-week CDA up to EOS follows the same approach as described in Section 5.4.2.1, but onset of progression is to be confirmed after 24 weeks (≥ 154 days, i.e., 168 days – two times 7-day visit time window) instead of after 12 weeks. The progression has to be persistent between onset and confirmation.

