5.5.3 Deaths

Death information (date of death and primary cause) is taken from the Death eCRF.

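### The CDA algorithm defines death due to MS differently in steps 2a and 4, so an MS-attributed death without a fatal relapse is an event only if an EDSS rise is still open

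*SAP*

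**What the plan says.** All of the rules are in SAP Section 5.4.2.1 unless another section is named.

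- **Step 2a** covers a rise that has no confirming visit: "If an EDSS increase cannot be confirmed due to no available EDSS assessment, but the subject dies due to MS". Its parenthesis then defines such a death: "experiences a relapse with outcome death, or death with reason 'Multiple sclerosis') the CDA is also considered confirmed". Onset is the initial EDSS rise and the death date serves as the confirmation date.
- **Step 2b** adds that every EDSS score between onset and confirmation must still meet the increase criteria.
- **Step 4** applies when no assessment has produced a CDA but the subject "dies due to MS (experiences a relapse with outcome death) the subject is considered to have a 12-week CDA". Onset is then the death date.
- **Step 5** takes everyone left over: "If no 12-week CDA is identified, the subject is considered censored with the censoring date derived according to the rules below". The rule that follows reads: "Censoring date is defined as: Date of last EDSS assessment without an EDSS increase".
- **Data sources.** The outcome of each relapse is recorded on the Relapse Summary eCRF (Section 5.4.1.1). Cause of death has a different source: "Death information (date of death and primary cause) is taken from the Death eCRF" (Section 5.5.3).
- **Reach.** The 24-week CDA derivation "follows the same approach as described in Section 5.4.2.1", with a longer confirmation interval (Section 5.4.4.1).
- **Use.** Sections 9.7 and 9.7.1 treat the analysis as exploratory. They plan event counts, Kaplan-Meier estimates, quartiles and a listing, with no treatment test.

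**The concern.** The same phrase has two closed definitions a few lines apart in one algorithm. Neither parenthesis is marked as an example, so a programmer would implement each as written. The criterion missing from step 4 is the recorded cause of death, which is a separate data item from relapse outcome. An MS-attributed death without a fatal-outcome relapse can therefore exist in the database.

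For such a death, event status depends on whether an EDSS rise happened to be open at the time. One subject contributes an event. Another with the same recorded cause of death is handled like an ordinary loss to follow-up, with a censoring date before the death. Section 4, which lists changes and clarifications and does address another part of the CDA derivation (the 90-day relapse cutoff), says nothing about this difference. If such a case arose, its coding could end up being decided after the treatment arm is known.

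**Working it through.** The plan gives no figure to reproduce on this point, so the check is a trace of the algorithm followed by a bound on the effect.

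**Trace.** Assume three subjects who each die on Day 200 with MS as the Death eCRF cause and no relapse with outcome death. The days are illustrative; Day 169 is the nominal Week 24 day in SAP Table 6.

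| Subject | Steps 2a and 2b | Step 4 | Result as written |
|---|---|---|---|
| A: qualifying rise at Day 169, no later EDSS | Met through the cause-of-death clause | Not needed | Event, onset Day 169 |
| B: no rise at any assessment up to Day 169 | No rise to confirm | Not met: no fatal-outcome relapse | Censored at Day 169 |
| C: earlier rise, back below the criteria at Day 169 | Not persistent | Not met | Censored at Day 169 |

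- If step 4 used the step 2a definition, B and C would be events at Day 200 and A would not change.
- If step 2a used the step 4 definition, A would not be confirmed. A would be censored at the last EDSS without an increase, or at randomization if there were none.

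**Size.** Inputs: 136 randomized subjects and a planned 1:1 allocation (SAP Section 2). Assumptions: equal arms, all subjects in the FAS, and zero or one affected death. The SAP gives no expected number of MS deaths.

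- Subjects per arm: 136 / 2 = 68.
- The Kaplan-Meier drop at one event is S(t−) / n(t), the survival estimate just before the event divided by the number at risk.
- With no censoring, S(t−) = n(t) / 68, so the drop is 1 / 68 = 0.0147, or about 1.5 percentage points at any time.
- With censoring the drop is larger. Assuming S(t−) = 0.93 and 20 subjects at risk, it is 0.93 / 20 = 0.0465, or about 4.7 percentage points.

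Follow-up is staggered and was cut short by early termination, so the 1.5-point figure is a lower bound for one event, not an estimate.

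**The case against.** The best defence is that the two steps deal with different evidence. In step 2a a measured worsening exists and the death stands in for a missing confirmation visit. In step 4 there is no confirmed worsening and the death alone creates the event, so a stricter requirement (a documented fatal relapse rather than a cause-of-death entry) is conceivable. This explains why the onset dates differ. It does not explain why the same term narrows, and the SAP does not offer it as a reason. What stands is that the text does not prove the broader definition was intended. It supports reconciling the two wordings or explaining the difference.

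The case is also narrow, and this stands in full. The subject must die with MS as recorded cause, have no fatal-outcome relapse, and have no qualifying rise open at death. The deviation code list shows that subjects had to be ambulatory with EDSS no higher than 6.0 at entry. EDSS is assessed every 12 weeks, and an acute MS death might well be recorded as a fatal relapse, which step 4 captures. All deaths are listed separately (Section 9.9.2.1), so a reader could find such a case.

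Three stronger readings are tempting and are not supported:

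- *Any earlier unconfirmed rise turns the death into an event.* Step 2a requires that no EDSS was available to confirm the rise and step 2b requires persistence, so a rise that had reverted (subject C) does not qualify.
- *The worst disability outcome is being scored as event-free.* No such subject is shown to exist.
- *Death sits at 10.0 on the EDSS, so every death should count.* Section 5.4.2.1 gives 10.0 only in describing the scale, and the analysis uses the score entered by the investigator. Nothing instructs anyone to enter 10.0 at death, and neither step treats all deaths as events.

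**Conclusion.** The inconsistency is real and follows from the text alone. Steps 2a and 4 give one term two meanings, and step 5 turns the difference into opposite event status for deaths with the same recorded cause. It affects 12-week CDA and, by reference, 24-week CDA.

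The practical weight is small. The most plausible effect is none, or a single event in an exploratory Kaplan-Meier summary with no planned test. One event is worth about 1.5 percentage points under the no-censoring assumption and 68 per arm, and about 4.7 points if it falls where 20 are at risk with survival at 0.93. The number of affected deaths and these risk sets are assumptions. The annualized relapse rate, the primary endpoint, does not use this algorithm. This is a wording correction worth making, not a threat to the study's conclusions.

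**What to change.** Before unblinding, use one definition of death due to MS in steps 2a and 4. The natural change is to extend the parenthesis in step 4 with the criterion already in step 2a, a Death eCRF reason of 'Multiple sclerosis', leaving the onset rules as they are. If the narrower step 4 rule is deliberate, state the reason there and describe the affected deaths differently, so that one term does not carry two meanings. Either change carries into 24-week CDA through Section 5.4.4.1.

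The cost is a few words in the SAP and one condition in the derivation program. No new data are needed, because cause of death is already collected.
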